1.1. Population to be analyzed

- In the protocol 15 patients are included in each group, with the ambition to reach totally 30 evaluable patients (per protocol), defined as patients completing the study. If a patient is excluded during or before the study, the patient will be replaced. Patients excluded from the study after inclusion will be accounted for as dropouts.
- The study will be performed in Norrköping.

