The alternative hypothesis is that we find a clinically relevant difference in fluid flows from the tissues and the pathway of fluid recruitment to the bloodstream.

Outcome Measures

Primary outcome variables are:

Recruitment of fluid from the interstitium calculated from fluid removal and hemoglobin changes.^{5,6}

Proportion of recruited fluid via lymph or via capillary/venular walls based on fluid recruitment and changes in plasma albumin and immunoglobulins G and M.

Secondary outcome variables are:

Weight, blood pressure and changes in bioimpedance variables.

Study Design

Open-label, prospective clinical observational study, where patients are divided into two groups. One group patients with sufficient urine production and dialysis performed solely to "purify" the blood, and another group without or with minimal urine production, who, in addition to blood purification, are in need of a significant fluid removal.

Number of Patients

The study population consists of 15 patients with minimal fluid removal during dialysis and 15 patients in need of fluid removal exceeding 2000 ml.

According to earlier experience, 15 patients in each group should be sufficient to clearly observe a pattern in fluid recruitment from the tissues (lymph or pericapillary fluid). For 80% power at 25% difference in fluid recruitment balance between the groups and a standard deviation of 20%, at least 11 patients should be recruited to each group to achieve a significance level below 0.05 with a T-test or Wilcoxon (if the material is not normally distributed).

Recruitment and Consent

Patients receiving hemodialysis regularly at the dialysis department at Vrinnevi Hospital in Norrköping are screened if they are expected to meet the inclusion criteria for the study.

Those who meet the inclusion criteria and have no exclusion criteria to participate are asked for participation and consent. Consent is obtained by one of the investigators verbally and in writing, during a hemodialysis session prior to the actual study procedure.

Inclusion Criteria:

Patients receiving hemodialysis (<500 ml or >2000 ml ultrafiltration):

Signed informed consent that the patient accepts participation in the study after oral and written information.

Exclusion Criteria:

Patients who may be affected by blood sampling, i.e., have low hemoglobin concentration, independent of dilution before dialysis (Hemoglobin 85 g/L).

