Patients who drink large amounts of water during regular dialysis (> 2 glasses, approximately 0.4 L).

The study is discontinued in case of a severe reaction (even if not related to the study), such as the need to interrupt dialysis. The patient or participant may also choose to discontinue participation in the study at any time.

Intervention and Procedures

Patients in need of dialysis and who regularly undergo dialysis at the dialysis unit at Vrinnevi Hospital in Norrköping are asked to participate in the study. Patients who are eligible are those who have fluid removal of either <500 ml or >2000 ml. These patients are approached during a routine dialysis visit to the dialysis unit. If the response is positive, a trial session is planned for a later date.

Before dialysis begins, the patient is weighed. Then, the regular dialysis procedure starts, with the dialysis machine being connected. At the same time, Bioimpedance is also connected to the patient, and values for lean body mass (LBM), fat mass (FM), ECV, and ICV are recorded. Pulse and blood pressure are also recorded. Once the dialysis machine is connected with an intravenous access, the first blood samples, i.e., "zero samples," are taken. Dialysis then commences.

The selected dialysate is recorded, as well as the continuous fluid removal and blood pressure. Blood samples are taken every 30 minutes for 150 minutes (Hb, hematocrit, albumin, Immunoglobulins G and M, and colloid osmotic pressure (COP)), bioimpedance values are recorded, and pulse and blood pressure are registered. This continues until the end of dialysis. At the end of dialysis, the final samples and measurements are taken. The patient is weighed once again.

Fluid intake if it occurs is also recorded. When the patient leaves the dialysis unit, the study concludes.

In case of pressure drops, these are treated in the usual manner, i.e., the patient is placed in the Trendelenburg position or supplemented with Albumin 20%. Measures are recorded.

In total, blood sampling amounts to approximately 50 ml, at most 75 ml, equivalent to 3 to 5 tablespoons.

Measurements

Weight is taken before and after dialysis.

Bioimpedance is connected and values for body composition, i.e., lean body mass (LBM), fat mass (FM), ECV, and ICV are recorded before and after dialysis, as well as during blood sampling.

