1.2. Statistical analysis

1.2.1. Statistical method

- A two-sided test of significance will be used.
- After the last patient has been included an evaluation will be made if results are distributed according to the norm. If so, parametrical statistical methods will be used i.e., T-test.
- If these are not distributed according to the norm the Wilcoxon test will be used.
- Recruitment of fluid is the primary variable.

If the study is dissected, it contains two groups:

- A. Patients with a fluid withdrawal of less than 500 ml
- B. Patients with a fluid withdrawal of more than 2000 ml

Statistical processing of the primary outcome

In the first analysis total recruitment of fluid from the tissues will be evaluated.

Total recruitment and AUC (Area under the curve) for recruited fluid, i.e., fluid removal and hemoglobin changes. Moreover, the inverted half-life for recruitment will be determined.

In the secondary analysis, the proportions of the fluid recruitments via lymph or via capillary/venular walls will be performed

Methods: One way test, T-test or Wilcoxon.

Secondary outcome

Weight, blood pressure and changes in bio-impedance variables will be correlated to withdrawal of fluid.

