1.2.2. Drop outs

Drop outs, i.e., included patients who do not complete the study, will be accounted for. However, to make up for the drop outs additional patients will be recruited.

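### Analysing only completers and replacing patients who stop can bias the refill estimates in the >2000 ml group, probably slightly and not always upward; no planned analysis uses data up to a stop.

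*SAP*

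**What the plan says.** - **Analysis population.** SAP 1.1 aims for "totally 30 evaluable patients (per protocol), defined as patients completing the study". It adds: "If a patient is excluded during or before the study, the patient will be replaced". The reason for exclusion makes no difference.
- **Dropouts.** SAP 1.2.2 says that dropouts will be accounted for, and continues: "However, to make up for the drop outs additional patients will be recruited". Neither document names an analysis of all started patients, of data up to a stop, or of sensitivity to dropout.
- **When participation ends.** Protocol, Exclusion Criteria: "The study is discontinued in case of a severe reaction (even if not related to the study), such as the need to interrupt dialysis".
- **Milder events.** Protocol, Intervention and Procedures: "In case of pressure drops, these are treated in the usual manner". The measures taken are recorded, and nothing removes these patients from the analysis.
- **Link to refill.** The Synopsis relates hypotension to low intravascular volume and insufficient reinfusion, and connects this with removal above 400 ml/hour. The Background names the fall in circulating volume as the main cause and says that recruitment protects against it.
- **Targets.** Purpose and Objectives includes the size and the rate of reinfusion. SAP 1.2.1 plans total recruitment and AUC, and adds: "Moreover, the inverted half-life for recruitment will be determined".
- **Data before a stop.** Intervention and Procedures has fluid removal recorded continuously. Measurements schedules samples at baseline, 1, 30, 60, 90 and 120 minutes, possibly 150, and at the end of dialysis.

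**The concern.** A patient whose session is interrupted may be one whose vascular space was not refilled fast enough, and refill is what the study sets out to measure. Replacing that patient with one who finishes would be selection related to the outcome. The reported size and rate of reinfusion would then describe only patients who tolerated the session. Counting dropouts shows that this happened but does not correct the estimates. Much of the information needed to examine it is already collected and would go unused.

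**Working it through.** **1. The plan's own figure.** SAP 1.4: difference 25, SD 20, two-sided 0.05, power 80%. Normal approximation: n = 2 × (1.960 + 0.842)² × (20/25)² = 10.05, rounded up to 11 per group, as stated. The exact t-test needs 11.09, with power 79.6% at 11 and 91.0% at the planned 15. Sample size is not the issue here; the SD of 20 is used in step 4.

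**2. Which group is exposed.** The documents give no session length.
- More than 2000 ml: 2000 / 400 = 5 hours, so any session of 5 hours or less averages above 400 ml/hour.
- Less than 500 ml: sampling to 120 minutes implies at least 2 hours, and 500 / 2 = 250, so the average is below 250 ml/hour.

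By the Synopsis's own threshold, refill-related stops would fall mainly in the >2000 ml group.

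**3. How often.** The Background's figure of about 10% counts sessions with hypotension, not interruptions. Assumed stop rate p = 2%, 5%, 10%. The expected number among 15 runs from 15 × 0.02 = 0.3 to 15 × 0.10 = 1.5. The chance of at least one, 1 − (1 − p)¹⁵, is 26%, 54% and 79%.

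**4. Shift of a completer mean.** Suppose the fraction p with the lowest tolerance stops, and tolerance has correlation ρ with refill. Shift = SD × ρ × φ(z_p) / (1 − p). With SD = 20:

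| p | ρ = 0 | ρ = 0.3 | ρ = 0.6 | ρ = 1.0 |
|---|---|---|---|---|
| 2% | 0 | 0.30 | 0.59 | 0.99 |
| 5% | 0 | 0.65 | 1.30 | 2.17 |
| 10% | 0 | 1.17 | 2.34 | 3.90 |

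The standard error of a group mean is 20/√15 = 5.16, so the shift is 0.06 to 0.76 standard errors. The SD shrinks by 0.5% to 16%. The corner value of 3.90 needs stopping to be fully determined by refill. The SD of 20 is the planning value for recruitment, not for refill fraction.

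**5. Direction by outcome scale.** Without diuresis and intake, the Protocol's formula is recruitment = ultrafiltrate + (PV_t − PV_0). Define refill fraction as recruitment / ultrafiltrate; this scale is introduced here and is not in the plan. Simulation with 2,000,000 draws per setting. Assumed: ultrafiltrate above 2000 ml with mean 2800 and SD 300 or 600; fraction with mean 0.80 and SD 0.05 or 0.10, independent of ultrafiltrate; p 2-10%; ρ 0.3-1.0.

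| Stops driven by | Refill fraction (percentage points) | Total recruitment (ml) |
|---|---|---|
| Plasma volume fall | +0.06 to +1.84 | −2.79% to +1.69% |
| Low fraction | up to 10 × 0.195 = +1.95 | +0.09% to +2.44% |
| Ultrafiltrate volume alone | unchanged | −0.20% to −5.27% |

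The volume-driven row depends on the assumed shape of the ultrafiltrate distribution; a normal shape cut off at 2000 ml gives a fall of at most about 3.7%. For a given session length, ml/hour is total ml divided by a constant, so its direction is equally uncertain. The simulation has no time dimension and says nothing about the half-life.

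**6. Effect on the group comparison.** Assumed mean recruitment is 0.80 × 2800 = 2240 ml. The largest shift is 0.0527 × 2240 = 118 ml, against 2000 − 500 = 1500 ml between the ultrafiltrate limits that define the groups. Ultrafiltrate is itself a term of the outcome.

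**The case against.** **The causal chain is inferred.** The Protocol stops participation for a severe reaction, treats pressure drops during the session, and never says that hypotension leads to interruption. It gives no interruption rate. This stands: stops before the session, or for unrelated reasons, cause no such bias.

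**The direction is not general.** A reader might infer that completers overstate the refill rate. The documents do not support that. Ultrafiltrate is part of recruitment, and if stops concentrate in patients with the largest volumes, completer ml and ml/hour come out too low. The upward direction holds only for refill fraction, which the plan does not estimate, and only if stops follow poor refill or plasma volume fall. This stands.

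**The planned rate measure was not modelled.** Neither the direction nor the size of any bias in the inverted half-life is known. This stands.

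**An interrupted patient does not lack a group today.** SAP 1.2.1 describes group B as "Patients with a fluid withdrawal of more than 2000 ml", so a reader might infer that a session stopped between 500 and 2000 ml belongs nowhere. Under the current SAP that patient is a dropout and needs no group. The Protocol also selects "15 patients in need of fluid removal exceeding 2000 ml", with eligibility settled beforehand. The gap matters mainly once stopped patients are kept.

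**Dropouts are already to be accounted for.** That commits the sponsor to reporting them, not to analysing their data, so it does not answer the point.

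**Conclusion.** The concern holds as a minor one. As written, the completer rule with replacement can select on refill, mainly in the >2000 ml group, and no planned analysis would show it. The completer estimates of size and rate of reinfusion can be biased: upward for refill fraction if stops follow poor refill or plasma volume fall, nil for that fraction if they follow volume alone, uncertain for total ml and ml/hour, and unassessed for the half-life.

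The size is unknown and probably small. Under the assumed 2-10% stop rate and the simulation inputs above, refill fraction moves by at most about 2 percentage points and total ml by a few percent in either direction. A reader might infer that the primary group comparison is compromised. That does not follow, because the groups are separated by a component of the outcome itself. Confidence is medium, since both the stop rate and its link to refill are assumptions.

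**What to change.** - **Analysis set (SAP 1.1, 1.2.2).** Keep every patient who starts the session and has a zero sample and at least one sample at 30 minutes or later, even if additional patients are recruited. A 1-minute sample alone should not qualify.
- **Group (SAP 1.2.1).** Assign by prescribed ultrafiltration, so that kept patients who stopped early have a group.
- **One supportive analysis.** Analyse recruitment to a pre-specified common time in all started patients who reached it, whether or not they finished. 120 minutes is a natural choice, being the last scheduled time that Measurements does not mark as optional.
- **Earlier stops.** Show the individual recruitment curves up to the stop, or include these patients through a repeated-measures model of the serial values. Do not carry the last rate forward: planning a half-life implies that the rate changes over time.
- **Reporting.** Give stops by group, time and reason, and label session total, AUC and half-life as completer estimates.

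The cost is a short SAP revision and slightly more analysis work, with no extra procedures and no change to any clinical stopping rule. The common-time result does not cover the later part of the session, and the session total, AUC and half-life remain uncorrected, though correctly labelled.

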1.2. Statistical analysis

1.2.1. Statistical method

- A two-sided test of significance will be used.
- After the last patient has been included an evaluation will be made if results are distributed according to the norm. If so, parametrical statistical methods will be used i.e., T-test.
- If these are not distributed according to the norm the Wilcoxon test will be used.
- Recruitment of fluid is the primary variable.

If the study is dissected, it contains two groups:

- A. Patients with a fluid withdrawal of less than 500 ml
- B. Patients with a fluid withdrawal of more than 2000 ml

Statistical processing of the primary outcome

In the first analysis total recruitment of fluid from the tissues will be evaluated.

Total recruitment and AUC (Area under the curve) for recruited fluid, i.e., fluid removal and hemoglobin changes. Moreover, the inverted half-life for recruitment will be determined.

In the secondary analysis, the proportions of the fluid recruitments via lymph or via capillary/venular walls will be performed

Methods: One way test, T-test or Wilcoxon.

Secondary outcome

Weight, blood pressure and changes in bio-impedance variables will be correlated to withdrawal of fluid.

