Blood volume (BV) at a later occasion, t , is calculated in a similar manor;

$$BV_t = \frac{MHb_t}{Hb_t}$$

Plasma volume (PV) is calculated;

$$BV_t (1 - Hct_t) = PV_t$$

The percentage increase/decrease in plasma volume will then be ($\Delta PV\%$);

$$\frac{PV_t - PV_0}{PV_0} \times 100 = \Delta PV\%$$

Recruited fluid (RE) from the tissue is based on the change in plasma volume and total diuresis/fluid removal. However, this volume must be corrected for diuresis and ingested fluid.

$$RE_{extravascular} = Ultrafiltrate + Diuresis - Ingested + (PV_t - PV_0)$$

Statistics and Data Processing

The study aims to follow a fluid kinetic process. In previous studies, we routinely used 10 healthy subjects to study similar processes. This has been sufficient to describe clear trends and differences in how the body responds to fluid infusions. However, in this study, we increase the number of participants to fifteen in each group to even more clearly establish the processes.

As there are only two groups to be compared, a t-test will primarily be used for the primary variable, i.e., the effect on plasma volume. For secondary variables, chi-square tests will be used. In the case of non-normally distributed data, Wilcoxon's test will be used instead.

Safety Regulation

The study will be conducted according to the protocol and applicable regulations, LVFS 2011:19, ICH GCP, and the latest version of the Helsinki Declaration. Patients will be monitored in the usual manner in the dialysis department.

Quality Assurance

- relevant health status data from medical records or health declaration
- signed consent
- The study is conducted in accordance with the protocol

Study Director [name] participated in a GCP course at Linköping University Hospital on April 25 - 26, 2007, and subsequently conducted several studies approved by the Medical Products Agency.

Ethics

Patients are approached for participation in a calm stage when they are receptive to information. If there is potential interest from the patient to participate, the study investigator informs the patient about the study. The responsible physician obtains the patient's written consent, and a copy of the signed consent form is provided to the patient.

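### Only the two ends of the ultrafiltration range are enrolled, so a correlation of secondary outcomes with fluid withdrawal over all patients would be enlarged by selection and would mostly restate the A-B difference

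*SAP*

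**What the plan says.** Eligibility is set by volume removed. The protocol (Intervention and Procedures) states: "Patients who are eligible are those who have fluid removal of either <500 ml or >2000 ml". The Inclusion Criteria give the same cut-offs, so nobody between 500 and 2000 ml can enter. The planned number is 15 per group (protocol, Number of Patients; SAP 1.1 and 1.4).

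SAP 1.2.1 builds the two groups on those cut-offs: "A. Patients with a fluid withdrawal of less than 500 ml" and "B. Patients with a fluid withdrawal of more than 2000 ml". The groups are not randomised and differ in more than volume. Under Study Design, one has sufficient urine output, and the protocol describes the other as "another group without or with minimal urine production".

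For the secondary outcomes, SAP 1.2.1 has one sentence: "Weight, blood pressure and changes in bio-impedance variables will be correlated to withdrawal of fluid". It names no coefficient, no within-group or group-adjusted analysis, and no limit on interpretation. SAP 1.3 mentions multiplicity only. The protocol (Statistics and Data Processing) names a different method: "For secondary variables, chi-square tests will be used", with Wilcoxon's test if the data are not normal.

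**The concern.** A correlation coefficient is a property of the relation and also of the spread of the x-variable in the sample. Leaving out the middle of the range and sampling the two ends 1:1 widens that spread, so any non-zero r rises. Changing to a rank coefficient does not cure this.

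With two separated clusters, r over all patients is also driven by the gap between the cluster means. It would come out clearly positive or negative if the two patient types differed for any reason, even with no relation between volume and response inside either group.

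The secondary results could therefore overstate how closely blood pressure or bioimpedance follows volume removed, and a difference between patient types could be read as a volume-response relation. That reading is tempting here, because the protocol (Risk-Benefit assessment) hopes the findings will help anticipate pressure falls. No patient between 500 and 2000 ml is available to check linearity.

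**Working it through.** **1. The plan's own figure.** The only sample-size figure is for the primary comparison (SAP 1.4): difference 25%, SD 20%, two-sided 0.05, power 80%.

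n = 2 × (1.960 + 0.842)² × (20/25)² = 2 × 7.85 × 0.64 = 10.05, rounded up to 11 per group.

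This reproduces the stated 11. An exact t-test calculation gives 11.09, with power 79.6% at 11 and 91.0% at 15 per group. None of this is affected by the present point.

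**2. Inputs for the correlation.** From the documents: cut-offs of 500 and 2000 ml, and 15 per group. Assumed, because the documents do not give it: the distribution of ultrafiltration in the unit. A linear relation with constant residual variance is also assumed.

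**3. Formulas.** Let k be the SD of ultrafiltration in the selected sample divided by the SD in the unit.

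- Selected variance (1:1 groups) = [(mean B − mean A)/2]² + (var A + var B)/2
- r_selected = r·k / √(r²k² + 1 − r²)
- Share between groups = first term of the selected variance / whole
- Within-group r: the same formula, with k = SD within the group / SD in the unit

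**4. One case by hand: uniform 0-4000 ml.**

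- Unit SD = 4000/√12 = 1155 ml.
- Group A: mean 250, variance 500²/12 = 20,833. Group B: mean 3000, variance 2000²/12 = 333,333.
- Between = (2750/2)² = 1,890,625. Within = (20,833 + 333,333)/2 = 177,083. Total 2,067,708, SD 1438 ml.
- k = 1438/1155 = 1.245. Share between groups = 1,890,625/2,067,708 = 0.914.
- For r = 0.30: 0.30 × 1.245 / √(0.09 × 1.551 + 0.91) = 0.374/1.025 = 0.365.
- r-squared ratio = 0.365²/0.30² = 1.48.

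**5. The same calculation for other assumed distributions, unit r = 0.30** (normals truncated at 0):

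| Assumed ultrafiltration (ml) | k | Pooled r | r² ratio | r within A | r within B | Between-group share |
|---|---|---|---|---|---|---|
| Bimodal: half uniform 0-800, half normal 2500/600 | 1.12 | 0.331 | 1.2 | 0.040 | 0.125 | 0.93 |
| Uniform 0-4000 | 1.25 | 0.365 | 1.5 | 0.039 | 0.155 | 0.91 |
| Uniform 0-3500 | 1.28 | 0.373 | 1.5 | 0.045 | 0.134 | 0.94 |
| Normal 2000/1000 | 1.41 | 0.406 | 1.8 | 0.047 | 0.197 | 0.89 |
| Normal 1500/900 | 1.47 | 0.419 | 2.0 | 0.055 | 0.175 | 0.92 |
| Normal 1800/800 | 1.54 | 0.435 | 2.1 | 0.056 | 0.180 | 0.92 |

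Over the same set, a unit correlation of 0.20 becomes 0.22-0.30 and 0.50 becomes 0.54-0.66. Under the truncated normals, a Spearman coefficient of about 0.29 becomes 0.39-0.41. The low within-group values here reflect restricted range only, because one linear relation was imposed. They do not show confounding. Step 6 does.

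**6. A group step and nothing else.** Simulated trials of 15 + 15, with A uniform 0-500 ml, B uniform 2000-4000 ml (assumed), and no relation with volume inside either group:

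| A-B difference (SD units) | Mean pooled r | Pooled test significant |
|---|---|---|
| 0 | 0.00 | 5.1% |
| 0.5 | 0.24 | 24% |
| 0.8 | 0.36 | 52% |
| 1.0 | 0.44 | 72% |
| 1.25 | 0.51 | 88% |

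The mean within-group r is 0 in every row. A check by formula for 0.8: the correlation of outcome with group label is 0.4/√(1 + 0.16) = 0.371, and that of group label with volume is √0.914 = 0.956. Their product is 0.355.

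**7. What adjustment can deliver.** With 91.4% of the volume variance between groups, adding a group term inflates the variance of the volume coefficient by 1/(1 − 0.914) ≈ 11.6, and its standard error by about 3.4. Within one group of 15, |r| must exceed 0.51 to be significant at 5%.

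**The case against.** The strongest reply is that the SAP never says the correlation is pooled. The protocol records fluid removal continuously, with blood pressure and bioimpedance at each half-hourly sample, so a within-patient or within-group correlation is also possible. This stands as far as it goes: pooling is an inference. But the sentence has no restriction to a group and no model, so one correlation over all patients is its natural reading. If something else is meant, the SAP has to say so.

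Second, the documents set no target correlation for dialysis patients in general. The hypotheses compare two groups, and enrolling the extremes is deliberate. This too stands in part: the enlargement matters only if r or r-squared is read beyond the sample. The dominance of the group gap does not depend on that target.

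Third, the size rests on an unknown distribution. A unit already split into two patient types would show little enlargement (0.30 to 0.33). This is correct, and the range has to include it. Weight change also fits the scenarios poorly: over a session it is largely the ultrafiltrate itself, so it should correlate strongly in any sample.

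A reader might infer more: that the pooled test produces too many false positives, that selecting on volume biases the regression slope, or that the primary result is compromised. None of these follows. With no association the test rejects in 5.1% of runs. Under a truly linear relation the slope is recovered. The primary analysis is a two-group comparison that does not use this correlation.

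**Conclusion.** The concern holds, for secondary outcomes only, and should be corrected. If the SAP sentence is carried out over all 30 patients, r and r-squared will exceed those in the unselected unit whenever a relation exists. For an r of 0.30 the result is about 0.33 to 0.43, or r-squared about 1.2 to 2.1 times as high. The direction is firm. The size depends on an assumed ultrafiltration distribution and a linear relation.

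The firmer finding is that about 90% of the ultrafiltration variance lies between the groups under every distribution tried. With A uniform on 0-500 ml and B uniform from 2000 ml, the share is 96% to 87% as B's upper limit goes from 3000 to 5000 ml. A pooled r is therefore close to a relabelled A-B comparison between non-randomised groups, and it cannot separate volume removed from patient type, including urine production. The SAP and protocol also name different methods for these outcomes.

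**What to change.** In SAP 1.2.1:

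- Make the A-B difference in each change (weight, blood pressure, each bioimpedance variable), with a 95% CI, the main secondary analysis.
- Report any relation with withdrawn volume as a slope per litre with a 95% CI, from a model with a group term or separately per group. Label it exploratory, because it will be very imprecise at 15 per group.
- If a pooled r or pooled slope is shown, state that it includes the group difference. A pooled slope alone is no remedy: in simple regression its p-value equals that of Pearson's r, and it carries the same confounding. State also that a pooled r does not describe dialysis patients in general.
- Reconcile the result with the chi-square sentence in the protocol's Statistics and Data Processing section, so that both documents name one method.

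The cost is wording only. No new data, visits or patients are needed. The downside is that the within-group estimates will be wide and will look less impressive than a pooled r.
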